9.2.3 Study visits

The abstracted data will be recorded on the case report form (CRF). **Table 1** shows the collected data at different retrospective period of the medical chart.

Table 1 Data collection schedule

| Variables | Time points | Eligibility assessment | Data collection retrospectively | | |
|----------------------------------|-------------|------------------------|---------------------------------|-------------------------|--------------------------------------|
| | | | Before the index date | Index date [#] | 1-year follow-up period [†] |
| Eligibility assessments | X | | | | |
| Demographics ¹ | | | | X* | |
| Diagnosis of COPD ² | | | | X* | |
| Smoking status ³ | | | | X* | |
| Comorbidity ^{4, §} | | X [◊] | X | X | |
| COPD assessments [‡] | | | | | |
| CAT ⁵ | | X ^Δ | X | X | |
| mMRC ⁶ | | X ^Δ | X | X | |
| Examinations [‡] | | | | | |
| Spirometry data ⁷ | | X ^Δ | X | X | |
| Eosinophils | | X ^Δ | X | X | |
| Records [‡] | | | | | |
| Acute exacerbations ⁸ | | X ^{&} | X | X | |
| Hospital admissions ⁹ | | X ^{&} | X | X | |
| Treatments | | | | | |

| Variables | Time points | Eligibility assessment | Data collection retrospectively | | |
|--|-------------|------------------------|---------------------------------|-------------------------|--------------------------------------|
| | | | Before the index date | Index date [#] | 1-year follow-up period [†] |
| Related to COPD ^{10, \$} | | | X ^{11, ♦} | X | X |
| Related to comorbidities ^{12, \$} | | | X [◊] | X | X |
| Rescue treatments ^{13, ‡} | | | X [◊] | X | X |
| Oxygen therapy ^{14, \$} | | | X [◊] | X | X |
| Others ^{15, \$} | | | X [◊] | X | X |

[#]Not later than 30 June 2018; defined as the date of COPD patients in the cohort A and B starting using LABA/LAMA therapy regardless of new initiation or switching from other single/dual/triple treatment, or the date of the patients in the cohort C starting using LAMA treatment

[†]Not later than 1 year after the index date

^{*}The data nearest to the index date will be collected.

[◊]The data 6 months before the index date will be documented.

^{\$}The data will be collected every 6 months (allowed window: ± 1 month).

[‡]All available data on the medical chart will be recorded.

[△]The data nearest to the index date will be collected as the **Baseline**.

[&]The data/events ever since patients started receiving LABA/LAMA or LAMA therapy will be collected (maximum: trace back to 1 year before the index date).

1. Date of birth, gender, race, BMI, occupation, and family history
2. Date of diagnosis and disease severity (GOLD grade: GOLD 1, 2, 3, 4; GOLD group: A, B, C. or D)
3. Former, current smoker, or non-smoker
4. Cardiovascular (e.g., ischemic heart disease, heart failure, coronary artery disease, myocardial infarction), cerebrovascular (e.g., stroke), respiratory (e.g., pulmonary hypertension), hepatic (e.g., hepatitis), renal (e.g., chronic kidney disease, kidney failure), gastrointestinal (e.g., GERD, GI bleeding, gastric disease), metabolic (e.g., diabetes mellitus [T1 or T2], hypertension, obesity, hyperlipidemia), infectious (e.g., pneumonia, respiratory tract infection, influenza, tuberculosis, viral infection), osteoporosis, anxiety, and depression.
5. Score between 0 – 40 points
6. Score between 0 – 4 points
7. FEV₁ and FVC, etc.
8. The definition of an acute exacerbation is that a complex of lower respiratory events/symptoms (worsening or new onset) related to the underlying COPD, with a duration of 3 days or more, requiring a prescription of antibiotics and/or systemic steroids and/or hospitalization (ICD-9: 491.21; ICD-10: J44.1). Onset/stop date, severity (mild, moderate, severe), and leading to hospitalization/acute respiratory failure (ICD-9-518.81 or ICD-10-J96.00/J96.01/ J96.02) or not will be recorded.
9. **Hospitalizations caused by COPD exacerbation (ICD-9: 491.21; ICD-10: J44.1)** will be collected only. The information includes admission/discharge date, treatments for COPD, and reasons for switching medications.
10. Including SABA (fenoterol, salbutamol, terbutaline), SAMA (ipratropium bromide), LABA (indacaterol, olodaterol), LAMA (aclidinium bromide, glycopyrronium, tiotropium, umeclidinium), LABA + LAMA (FDC; tiotropium/olodaterol, indacaterol/glycopyrronium, vilanterol/umeclidinium), LABA + ICS (formoterol/beclothesone, formoterol/budesonide, salmeterol/fluticasone, vilanterol/fluticasone), triple therapies (free combo or vilanterol/umeclidinium/fluticasone [FDC]), or others (theophylline, roflumilast, mucolytics, etc.). Prescription date, doses, frequency, and reasons for switching medications will be recorded.

| Variables | Time points | Eligibility assessment | Data collection retrospectively | | |
|-----------|---|------------------------|---------------------------------|-------------------------|--------------------------------------|
| | | | Before the index date | Index date [#] | 1-year follow-up period [†] |
| 11. | If a patient receiving SABA, SAMA, LABA/ICS or a triple therapy before LABA/LAMA treatment on the index date, the relevant information on the medications, doses, frequency, the route of administration, the reasons for switching medications should be recorded. | | | | |
| 12. | Prescription date, doses, and frequency will be recorded. | | | | |
| 13. | Therapies for the emergency/hospitalization regarding COPD (ICD-9: 491.21; ICD-10: J44.1) will be collected, including but not limited to short-acting bronchodilators, antibiotics, oral corticosteroid (e.g., prednisone or prednisolone), ventilator support, or oxygen therapy. Prescription date, doses, frequency, and the route of administration will be recorded. | | | | |
| 14. | NIPPV or IPPV for those not for rescue use | | | | |
| 15. | Including but not limited to surgeries for COPD or improvement of lung function. | | | | |

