| Variables: | 
Variables
 
• Patient demographics (date of birth, gender, race, body mass index [BMI], family history, occupation, etc.)• Diagnosis of COPD (date of diagnosis, disease severity, etc.)• Smoking status• Spirometry data (e.g., FEV₁, FVC)• COPD assessments (e.g., CAT, mMRC)• Acute exacerbations from 1 year before the index date until 1 year after the index date or the date of death (onset/stop date, etc.)• Hospitalizations due to COPD exacerbation (e.g., admission/discharge date, treatments)• Laboratory data (e.g., eosinophil counts) |

Proprietary confidential information © 2019 Boehringer Ingelheim International GmbH or one or more of its affiliated companies

| | |
|-----------------------|--|
| | 
• Pharmacological/non-pharmacological treatments from 6 months before the index date to 1 year after the index date or the date of death, especially for the following:
- Treatment related to COPD (start/stop dates, dosage, frequency, etc.)- Rescue treatments for COPD (antibiotics, oral corticosteroid, ventilator support, etc.)- Oxygen therapies- Surgeries for COPD therapy or improvement of lung function• Time/reasons for treatment switching (e.g., single/dual/triple therapy to LABA/LAMA prior to the index date, Tio + Olo to other therapies, single/dual escalating to dual/triple therapy)• Comorbidities (cardiovascular, cerebrovascular, respiratory, hepatic, renal, gastrointestinal, metabolic, infectious comorbidities, etc.) |
| | 
Primary outcomes
 
• Time to the first moderate or severe COPD exacerbation |
| | 
Secondary outcomes
 
• Annualized rate of mild/moderate/severe exacerbation• Time/reason (e.g., severe airflow limitation, diagnosis of asthma, worsening exacerbation) from LABA/LAMA escalating to LABA/LAMA/ICS or from LAMA to dual therapy• Percentage of patients receiving LABA/LAMA switched to triple therapy or LAMA switched to dual therapy• Change in pulmonary function after LABA/LAMA or LAMA initiation• Use of rescue medications |
| Data sources: | Source data are collected from medical charts in 12 medical hospitals in Taiwan. The case report form (CRF) will be designed for the data collection. |
| Study size: | Approximately 1,800 eligible COPD patients are planned to be enrolled from 12 medical hospitals in Taiwan. |

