9. RESEARCH METHODS

9.1 STUDY DESIGN

It is a retrospective, multi-center, cohort study to collect the data on COPD patients who were administered with LABA/LAMA (FDC or free combo) or LAMA therapy for 3 months at least prior to 30 June 2018. The patients using LABA/LAMA therapy will be enrolled regardless of new initiation or switched from other single/dual/triple treatment, whereas those using LAMA treatment will only be acceptable when LAMA is newly initiated. This study aims to estimate the occurrence of COPD exacerbation in the COPD population under the real-world practice in Taiwan. Additionally, the study also assesses outcomes of clinical characteristics and prescription patterns for patients using LABA/LAMA or LAMA. After Institutional Review Board's (IRB) permission, it will be carried out in around 12 medical centers in Taiwan and plans to collect the clinical data abstracted from the medical charts of approximately 1,800 eligible patients. The eligible patients will be separated into three cohorts based on the prescription for COPD on the index date. Cohort A includes the patients treated with Tio + Olo, cohort B is the patients treated with other LABA/LAMA therapy, and cohort C is the patients receiving LAMA treatment. No investigational or interventional treatment will be provided in the retrospective study.

The retrospective study will review medical charts of COPD patients with LABA/LAMA or LAMA therapy until death or 1 year after the index date, whichever occurs first. The data collection will be conducted after eligibility assessment. Medical records will be reviewed and relevant information will be abstracted for various details such as patient demographics, diagnosis of COPD, smoking status, records of exacerbations and hospitalization, examinations of lung function and laboratory, treatments related to COPD or comorbidities, reasons for treatment switching, and comorbidities.

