9.3.3.3 Acute exacerbation of COPD

The data from 1 year before the index date until death or 1 year after the index date should be collected.

Acute exacerbation is defined as a complex of lower respiratory events/symptoms (worsening or new onset) related to the underlying COPD, with a duration of 3 days or more, requiring a prescription of antibiotics and/or systemic steroids and/or hospitalization (should all be accompanied by code of ICD-9-491.21 or ICD-10-J44.1). Within the retrospective period, the onset/stop date of COPD exacerbation, severity* (mild, moderate, severe), and its outcome (leading to hospitalization/acute respiratory failure [ICD-9-518.81 or ICD-10-J96.00/J96.01/J96.02] or not) will be recorded. In terms of the exacerbation-related therapies, they will be recorded onto the page of “Rescue treatments” in the CRF.

***Mild exacerbation** is a patient with worsening but self-managed symptoms.

Moderate exacerbation is a patient receiving an exacerbation-related prescription such as oral corticosteroid (prednisone or prednisolone) and/or antibiotic, but not requiring hospitalization.

Severe exacerbation is a patient requiring hospitalization or emergency room visit due to COPD (ICD-9-491.21 or ICD-10-J44.1).

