9.7.1 Main analysis

The propensity score matching approach* will be used to balance the baseline characteristics between the study cohorts. These data will be compared descriptively between patients receiving different regimens (Tio + Olo vs. other LABA/LAMA vs. LAMA). If the propensity score matching is done, the difference before and after matching will be considered both.

For the primary outcome

Time to the first moderate or severe COPD exacerbation will be compared between different cohorts using Kaplan-Meier curves with the incidence and time to events, and statistical significance will be assessed using log-rank tests.

Time to first acute exacerbation starts from the index date to the date of the first acute exacerbation recorded on the CRF. Patients with exacerbation free at the time of escalating to ICS or no documented with exacerbations will be censored.

For secondary outcomes

- Time to escalating to dual/triple therapy will also be analysed using Kaplan-Meier curves and log-rank tests.
- The annualized rate of exacerbation with various severity will be calculated for each study group (episodes/patient-year), and the differences between the three cohorts will be compared by rate ratio.
- Results of lung function (i.e., spirometry data) and COPD assessments (i.e., CAT and mMRC) will be evaluated by the change from baseline. Pair *t*-test or other applicable statistical methods will be used for assessing the intra-group difference under a significance level of 0.05.
- Chi-square test or Fisher's exact test will be applied for categorical variables such as reasons for switching/escalating therapies, frequency, and percentage, etc.

*NOTE: Variables may include but not limited to age, gender, disease duration before index date, smoking status, body mass index, COPD assessment score (e.g., CAT and mMRC), spirometry data (e.g., FEV₁), oxygen therapy, comorbidities, disease severity, previous exacerbation, previous treatments, or eosinophil counts, where appropriate.

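### The Table 1 footnote ties pre-index exacerbation history to the start of LAMA-containing therapy, contradicting the unconditional 1-year look-back elsewhere and making a candidate matching variable non-comparable between cohorts

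*Combined protocol and SAP*

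**What the plan says.** Table 1 in section 9.2.3 marks acute exacerbations and hospital admissions for collection before the index date, and both marks carry the same footnote: "The data/events ever since patients started receiving LABA/LAMA or LAMA therapy will be collected", followed by "maximum: trace back to 1 year before the index date" in parentheses.

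The same table sets the index date. For cohorts A and B it is "defined as the date of COPD patients in the cohort A and B starting using LABA/LAMA therapy regardless of new initiation or switching"; for cohort C it is "the date of the patients in the cohort C starting using LAMA treatment". Section 9.1 adds that "those using LAMA treatment will only be acceptable when LAMA is newly initiated".

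Three other places give a look-back that does not depend on treatment:

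- The abstract, under variables: "Acute exacerbations from 1 year before the index date until 1 year after the index date or the date of death".
- Section 9.3.3.3, on exacerbations: "The data from 1 year before the index date until death or 1 year after the index date should be collected".
- Section 9.3.3.2, item 4, which sets the same 1-year period for hospitalization records.

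Section 9.7.1 lists candidate variables for the propensity score, among them "disease severity, previous exacerbation, previous treatments". The list is open-ended and gives no look-back length for any history variable. Sections 9.7 and 9.7.3 rule out imputation.

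**The concern.** The footnote starts the clock at first use of LABA/LAMA or LAMA, and the index date is that first use for many patients. A rule meant to describe history before index therefore leaves some patients with no history to collect. Whether a patient has a window depends on earlier treatment, and earlier treatment is linked to cohort: cohort C admits only new LAMA starters, while A and B also admit switchers.

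This matters because the cohorts are not randomized and matching is the planned remedy for imbalance (sections 9.7.1 and 9.9). The primary outcome is time to first moderate or severe exacerbation, and exacerbation history is a direct measure of prior risk for that outcome. If history is recorded under different rules in different cohorts, matching on it aligns recording practice and not risk. If it is missing in one cohort, it cannot be used there at all. The comparisons with LAMA are the most exposed.

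**Working it through.** There is no stated figure to reproduce. The check compares the two collection windows patient type by patient type.

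**Inputs.** Footnote rule, ceiling and index date from section 9.2.3; entry rule for cohort C from section 9.1; 1-year look-back from the abstract and sections 9.3.3.2 and 9.3.3.3.

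**Formulas.**
- Footnote window = min(365 days, index date − first start of LABA/LAMA or LAMA).
- Window in the other three places = 365 days for everyone, as far as the chart holds the data.

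| Patient | Footnote window (days) | Other sections (days) |
|---|---|---|
| Cohort C (new LAMA starters only) | 0 | 365 |
| A or B, new initiator | 0 | 365 |
| A or B, switched from therapy without a LAMA (e.g. LABA/ICS) | 0 | 365 |
| A or B, switched from LAMA-containing therapy | up to 365, by time since its start | 365 |

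The rules differ by up to 365 days per patient. Under the footnote cohort C always has 0, whereas A and B range from 0 to 365.

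A narrower reading takes the start to mean the start of the index therapy itself. Then the window is 0 for everyone, and both the pre-index mark and the 1-year ceiling have no function. That reading also contradicts the other three places.

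**Illustration of what is lost.** Assume that pre-index events follow a Poisson process at the planning rates in section 9.5, 0.78 and 0.90 per patient-year. These are rates assumed for the study treatments; the documents give no pre-index rate. Expected events = rate × days/365, and P(at least one) = 1 − exp(−expected events).

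| Days collected | Expected events per patient | P(at least one recorded) |
|---|---|---|
| 0 | 0 | 0% |
| 182 | 0.39 to 0.45 | 32% to 36% |
| 365 | 0.78 to 0.90 | 54% to 59% |

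For a full year: 1 − exp(−0.78) = 0.542 and 1 − exp(−0.90) = 0.593. Patients with identical underlying risk would thus show different recorded histories purely by how long they had been on earlier LAMA-containing therapy.

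**The case against.** The strongest reply is that the footnote is only badly worded. Its parenthesis names 1 year before index, three other places state that period plainly, and a pre-index mark that is empty for all of cohort C would be pointless. This makes a 1-year intention plausible. It does not remove the conflict: the parenthesis sets a maximum, and a maximum gives no days to a patient whose therapy began on the index date. The general footnote asking for all available chart data sets no pre-index window either.

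A second reply is that the history is not wholly lost. Table 1 collects rescue treatments for 6 months before index in every cohort, with prescription dates, and section 9.3.3.3 sends exacerbation-related therapies to that CRF page. This stands, but it covers half of the year and records treatments, not dated and graded exacerbations.

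Some stronger readings go beyond the documents:

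- A reader might infer that the plan matches on a 1-year exacerbation history. Section 9.7.1 only says that the variable may be included, and gives no look-back.
- A reader might infer that cohort C would be coded as having no prior exacerbations. Nothing says that uncollected history becomes zero; with imputation barred it could equally be missing.
- A reader might infer that many A and B patients would have a populated history. No share of switchers is given, and those switching from therapy without a LAMA would have none.
- A reader might take cohort C to be 700 patients. That is subtraction from approximate figures (1,800 − 300 − 800); the protocol states no size for it, and the point does not depend on it.

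**Conclusion.** The contradiction is real and should be resolved before the propensity score is built. Taken literally, the footnote gives 0 pre-index days to cohort C and to A and B patients without earlier LAMA-containing therapy, and up to 365 days to the other switchers; the abstract and sections 9.3.3.2 and 9.3.3.3 give 365 days to all. It affects COPD-exacerbation admissions as well as exacerbations.

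The consequence is conditional. If sites followed the footnote, previous exacerbation would be missing or zero by cohort because of the recording rule and could not serve as a comparable matching covariate. If sites followed the other sections, the harm did not occur and only the wording needs repair. The documents do not show which rule sites or the CRF applied, so they do not support saying that the data are already biased. The 54% to 59% figure rests on the Poisson model and on borrowing the planning rates; it indicates scale only.

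**What to change.** 1. Reword the Table 1 footnote to collect all exacerbations and COPD-exacerbation admissions from 1 year before the index date, regardless of treatment at the time, as available in the chart.
2. In section 9.7.1, state that previous exacerbation, if used in the propensity score, is measured over that same 1-year look-back.
3. Confirm with each site, and from the CRF instructions, which rule was applied.

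The wording change is cheap, because the 1-year abstraction is already required elsewhere in the protocol. The possible cost is in the data. This version is dated 25 November 2019, and section 6 plans collection from 1 August to 30 November 2019, so charts may already have been abstracted. Any abstracted under the footnote would need the pre-index year completed. Where that cannot be done, the variable should be left out of the matching for comparisons in which it was not collected alike, and the report should say so. The price is then that a direct measure of prior risk goes unadjusted in those comparisons.

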9.2.4 Study discontinuation

Boehringer Ingelheim reserves the right to discontinue the study overall or at a particular study site at any time for the following reasons:

- Violation of Good Clinical Practice (GCP), the study protocol, or the contract by a study site or investigator, disturbing the appropriate conduct of the study

The investigator/the study site will be reimbursed for reasonable expenses incurred in case of study termination (except in case of the third reason).

9.3 VARIABLES

9.3.1 Exposures

Not applicable.

9.3.2 Outcomes

9.3.2.1 Primary outcomes

- Time to the first moderate or severe COPD exacerbation

9.3.2.2 Secondary outcomes

- Annualized rate of mild/moderate/severe exacerbation
- Time/reason (e.g., severe airflow limitation, diagnosis of asthma, worsening exacerbation) from LABA/LAMA escalating to LABA/LAMA/ICS or from LAMA to dual therapy

Proprietary confidential information © 2019 Boehringer Ingelheim International GmbH or one or more of its affiliated companies

- Percentage of patients receiving LABA/LAMA switched to triple therapy or LAMA switched to dual therapy
- Change in pulmonary function after LABA/LAMA or LAMA initiation
- Use of rescue medications

9.3.3 Covariates

9.3.3.1 Eligibility assessments

The eligibility should be checked by investigators before the data collection (see **Section 9.2.2** in detail). The following assessments are conducted to determine the eligibility for each patient:

1. Review the medical chart to confirm if a subject with COPD were prescribed with LABA/LAMA or LAMA therapy for 3 months at least (not later than 30 June 2018). Additionally, a subject must be ≥ 40 years of age.
2. Check the medical chart to exclude the patient with bronchial asthma, ACOS, bronchiectasis, cystic fibrosis, or lung cancer

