| Study design: | 
This is a retrospective, multi-center, cohort study to collect the data on COPD patients who were administered with LABA/LAMA (FDC or free combo) or LAMA treatment for 3 months at least prior to 30 June 2018. For LABA/LAMA therapy, new initiation or switching from other therapy (i.e., single/dual/triple) are both acceptable; for LAMA
 | | |

Proprietary confidential information © 2019 Boehringer Ingelheim International GmbH or one or more of its affiliated companies

| | |
|--------------------|---|
| | 
treatment, only new initiation will be acceptable. The data abstracted from eligible patients will be recorded only when they are available in the medical chart and will be categorized into the cohort A (patients treated with Tio + Olo), B (patients treated with other LABA/LAMA therapy), and C (LAMA therapy).
 
The follow-up period for each patient will be from the index date* until the date of death or 1 year after the index date, whichever occurs first. Patients will be censored at the time from one LAMA/LABA or LAMA switched to another LAMA/LABA or ICS.
 
*Index date: It is defined as the date of COPD patients in the cohort A and B starting using LABA/LAMA therapy regardless of new initiation or switching from other single/dual/triple treatment, or the date of the patients in the cohort C starting using LAMA treatment.
 |
| Population: | 
This study plans to review the medical chart from approximately 1,800 COPD patients receiving LABA/LAMA or LAMA treatment for 3 months at least prior to June 30 2018 in Taiwan.
 
Inclusion criteria
 
Patients who fulfil ALL the following criteria are included.
 
1. Patients who diagnosed with COPD who were prescribed with LABA/LAMA (FDC or free combo) as a new initiation or switching from other therapy (i.e., single/dual/triple), or newly receiving LAMA treatment for 3 months at least prior to 30 June 20182. Male or female patients ≥ 40 years of age 
Exclusion criteria
 
Patients who meet the following criterion are not included.
 
1. Patients with documented diagnosis of bronchial asthma, asthma-COPD overlap syndrome (ACOS), bronchiectasis, cystic fibrosis, or lung cancer |

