9.2.2 Study population

The data will be retrospectively abstracted from the medical chart after eligibility assessment. Eligible patients will be categorized into the cohort A (patients treated with Tio + Olo), B (patients treated with other LABA/LAMA therapy), and C (patients treated with LAMA therapy).

Inclusion criteria

Patients who fulfil **ALL** the following criteria are included.

1. Patients who diagnosed with COPD who were prescribed with LABA/LAMA (FDC or free combo) as a new initiation or switching from other therapy (i.e., single/dual/triple), or newly receiving LAMA treatment for 3 months at least prior to 30 June 2018
2. Male or female patients ≥ 40 years of age

Exclusion criteria

Patients who meet the following criterion are not included.

1. Patients with documented diagnosis of bronchial asthma, asthma-COPD overlap syndrome (ACOS), bronchiectasis, cystic fibrosis, or lung cancer

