9.7 DATA ANALYSIS

Statistical analyses will be conducted by the designated personnel. The main analysis population will consist of all eligible patients (i.e., all patients fulfilling all inclusion criteria and no exclusion criterion).

Descriptive analyses will be performed to summarize patient baseline characteristics, the observation period, the time to exacerbation/or to escalating to triple therapy, and the rates of exacerbation, etc. Continuous variables include number, mean, median, standard deviation (SD), range (minimum and maximum value), and 95% confidence intervals (CI). Categorical variables are frequency and percentage.

Statistical analysis of all data will be performed using the latest version of SAS® statistical software (SAS Institute, Cary, NC, USA) or other commercially available standard statistical software.

All information already collected as part of the study will be retained for further analyses; however, no extra efforts will be made to obtain or record additional information regarding the patient. In general, data imputation will not be permitted for any analyses in this study.

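### On its most natural reading, the entry rule needs 3 months on therapy while the primary clock starts on day 1, so a post-index condition selects who is analysed; direction and size of the bias are unknown

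*Combined protocol and SAP*

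**What the plan says.** **Entry.** The site check in section 9.3.3.1 takes patients "prescribed with LABA/LAMA or LAMA therapy for 3 months at least (not later than 30 June 2018". Section 9.1 describes patients "administered with LABA/LAMA (FDC or free combo) or LAMA therapy for 3 months at least prior to 30 June 2018", and the Abstract is similar. Inclusion criterion 1 in section 9.2.2 lists LABA/LAMA first and ends with "newly receiving LAMA treatment for 3 months at least prior to 30 June 2018".

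**Index date.** The Table 1 footnote in section 9.2.3 gives "Not later than 30 June 2018; defined as the date of COPD patients in the cohort A and B starting using LABA/LAMA therapy". For cohort C it is the day LAMA starts. The Abstract and section 9.3.3.2 agree that index is the start of therapy.

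**Clock and population.** Section 9.7.1: "Time to first acute exacerbation starts from the index date to the date of the first acute exacerbation recorded on the CRF". Section 9.7: "The main analysis population will consist of all eligible patients".

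**Patients who leave.** The Abstract runs follow-up to death or 1 year after index and adds "Patients will be censored at the time from one LAMA/LABA or LAMA switched to another LAMA/LABA or ICS". Section 9.7.1 censors event-free patients at escalation to ICS.

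**Adjustment and limitations.** Section 9.7.1 plans propensity matching on baseline variables. Section 9.9 discusses data availability, baseline imbalance and the patient pool, and calls the entry criteria non-restrictive. The contents page has one redacted entry between 9.7.1 and 9.7.3.

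**The concern.** Therapy begins on the index date, so 3 months of it can only be completed afterwards. If that duration is required for entry, what happens after time zero decides who is analysed. Follow-up is allowed to end in death at any time after index, yet a death in months 0-3 could never be seen.

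The primary objective (section 8) is the occurrence of exacerbations in treated patients. It would be estimated only in patients who lasted 3 months. If early loss is related to exacerbation, the estimate is biased. If that relation differs by cohort, the cohort ratios shift too. Matching on baseline variables cannot undo selection on later events.

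**Working it through.** **1. What the wording allows**

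| Reading of the 3-month clause | Who is lost in months 0-3 |
|---|---|
| Time on therapy, counted at class level | Deaths; patients who stop or leave both classes |
| Time on therapy, on the index regimen | The above, plus patients who escalate or switch |
| Clause attaches to LAMA only (section 9.2.2 syntax) | As above, in cohort C only |
| Therapy started at least 3 months before 30 June 2018 | Nobody |

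Section 9.3.3.1 puts the calendar date in its own bracket, and section 9.1 speaks of therapy being administered for the period. Both favour time on therapy. The latest index date is also unclear: 30 June 2018 in Table 1, but about the end of March 2018 if 3 months must be completed before 30 June.

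**2. The plan's own figure**

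Section 9.5 assumes 0.78 and 0.90 events per patient-year; 0.78/0.90 = 0.867, printed as 0.87. The printed interval (0.768, 0.978) is reproduced by 0.867 × exp(±1.96 × √(1/(0.78×300×T) + 1/(0.90×800×T))) at T = 1.5 patient-years. The stated T of about 2 gives (0.781, 0.962). That is a separate matter. Only the two rates are used below.

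**3. Illustration**

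Assumptions: the section 9.5 rates serve as constant first-event hazards r; follow-up is 1 year; a = 0.25 year. A share p of patients with a first event in months 0-3 is removed, and a share q of those event-free at month 3. The documents give neither p nor q.

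- Early group: E0 = 1 − e^(−ar); PT0 = (1 − e^(−ar)(1 + ar))/r
- Event-free at month 3: S = e^(−ar); E1 = S − e^(−r); PT1 = aS + (S − e^(−r))/r
- Measured rate = [(1−p)E0 + (1−q)E1] / [(1−p)PT0 + (1−q)PT1]

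At r = 0.90: E0 = 0.2015, PT0 = 0.0242, S = 0.7985, E1 = 0.3919, PT1 = 0.6351.

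| p | q | Events / time | Measured rate |
|---|---|---|---|
| 0 | 0 | 0.5934 / 0.6594 | 0.90 |
| 10% | 0 | 0.5733 / 0.6569 | 0.87 |
| 30% | 10% | 0.4938 / 0.5886 | 0.84 |
| 10% | 10% | 0.5341 / 0.5934 | 0.90 |
| 10% | 20% | 0.4949 / 0.5299 | 0.93 |

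Extreme bounds when 10% of starters are excluded are 0.76 to 0.94. The lower end needs p = 0.10/0.2015 = 50% with q = 0; the upper end needs p = 0 with q = 0.10/0.7985 = 12.5%. At r = 0.78 the bounds are 0.65 to 0.81, and the lower end needs p = 56%.

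**4. Cohort ratios with no true difference (r = 0.90)**

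- Only early exacerbators removed, 10% against 30%: 0.873/0.817 = 1.07; reversed, 0.94.
- Event-free patients also removed at half those shares: 1.04; reversed, 0.96.
- Removal unrelated to exacerbation: 1.00.
- Rule applied to cohort C only, ratio of A or B over C: 0.900/0.817 = 1.10 (p = 30%, q = 0); 0.900/0.934 = 0.96 (p = 10%, q = 20%).

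**5. Escalation outcomes, only if the 3 months must be on the index regimen**

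No escalation can then occur in months 0-3. With constant hazard h = −ln(1 − true share), the measured 1-year share is 1 − e^(−0.75h). True shares of 10%, 20% and 30% become 7.6%, 15.4% and 23.5%.

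**The case against.** **The clause may not select at all.** It can be read as a calendar condition, or as applying to LAMA only. This stands, and it is why everything below is conditional on the reading. It does not remove the need to act: around 12 hospitals could apply different rules, and the LAMA-only reading bears directly on the cohort comparison.

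**Restricting to established users can be legitimate.** It can, but the plan should then say so. As written, it starts the clock earlier and calls entry non-restrictive.

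**This is not immortal-time bias in full.** Correct. A reader might infer that months 0-3 are event-free by construction. For exacerbations they are not: events in retained patients count from day 1. Only survival and staying on therapy are conditioned on.

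**A reader might infer that exacerbations are understated**, because section 9.3.2.2 includes "Time/reason (e.g., severe airflow limitation, diagnosis of asthma, worsening exacerbation) from LABA/LAMA escalating to LABA/LAMA/ICS or from LAMA to dual therapy". The documents do not support a direction. Those moves remove a patient only if the 3 months must be on the index regimen. Section 9.3.3.1 is worded at class level, and at that level escalators can stay in and be censored. Nor does the list show that patients leaving for the other reasons are event-free, so it does not establish overstatement either.

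**The extreme bounds overstate the likely size.** This also stands. The 0.76 needs about half of early exacerbators, and nobody else, removed. The milder scenarios move the rate by about 3-4%.

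**An analysis may sit in the redacted section.** That cannot be ruled out.

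**Conclusion.** The point holds, with medium confidence, on the reading that the 3 months is time on therapy. Patients who die or stop therapy in months 0-3 are then selected out by a post-index condition; those who escalate or switch are lost too only at regimen level. Baseline matching cannot correct this, and the readable analysis text and section 9.9 are silent.

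Neither direction nor size can be determined. A true 0.90 per year is measured as 0.87 to 0.93 in the milder scenarios and as 0.90 if removal is unrelated to exacerbation. These figures rest on assumed removal shares and on annualised rates used as first-event hazards, so they show what is possible and do not predict a size. The documents give no early-loss figures by cohort, so a claim that any one cohort is favoured would go beyond them.

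**What to change.** 1. Reconcile the Abstract and sections 9.1, 9.2.2, 9.2.3 and 9.3.3.1 into one rule: whether the 3 months is time on therapy, which cohorts it covers, whether it is counted at class or regimen level, and the latest index date. Section 6 ends data collection on 30 November 2019, so also record which reading each site applied and tabulate time on therapy by cohort and site. A site with no patient under 3 months probably applied it as time on therapy.

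2. If the rule is time on therapy, pre-specify a sensitivity analysis of the time-to-event, rate and escalation outcomes with time at risk starting at index + 3 months. Include patients who at that point are alive, uncensored and meet the same therapy condition as the reconciled entry rule; for first-event outcomes they must also be event-free. Report it beside the index-date analysis.

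3. Only if the rule is time on therapy, state in section 9.9, for the cohorts covered, that the estimates apply to 3-month persisters and that the direction of the selection bias is unknown.

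**Cost.** Wording, one tabulation and one added analysis. The month-3 analysis loses first events: (1 − e^(−0.25r))/(1 − e^(−r)) = 34% at 0.90 and 33% at 0.78. If risk varies between patients (gamma frailty with variance 1, S(t) = 1/(1 + rt)), the loss is 39% and 37%. Intervals on the log scale widen by 1/√(1 − loss), about 1.2 to 1.3 times.

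The CRF must hold stop or repeat-prescription dates. The Abstract lists start and stop dates, but section 9.3.3.7 lists prescription dates recorded every 6 months, so this needs checking. The excluded patients are not recovered, and a sample built on mixed readings can only be reported as such.
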